To assess bone quality and its effect on glenoid component loosening, we will take trabecular bone samples from all patients. Humeral heads, which are normally discarded as standard of care medical waste will be kept and evaluated with mechanical testing. These bone samples will be assessed by micro CT to measure trabecular bone volume and connectivity as well as by mechanical testing. This data will be correlated with the trabecular bone volume of the glenoid defined by the pre-operative CT scans. In addition all bone quality measurements will be correlated with CT scan imaging of the glenoid at the time of surgery and at two year follow up.

Patient Enrollment

The proposed clinical study will enroll patients indicated for standard of care anatomic total shoulder arthroplasty. They will receive all pre-operative testing, intra-operative care including all implants and post-operative care that is standard of care and specific to the surgeon and patients decisions for care. The only change for the case series will be the type of surgical instruments used to place the glenoid guide pin, coring of the bone to obtain bone tissue, placement of the beads and post-operative CT scanning. In all cases the surgeon is able and allowed to use their own surgical judgment to place the guide pin, prepare the bone and place the desired implant. In all cases, the surgeon can use any and all of the standard instruments or guides provided by the implant manufacturer as the surgeon would use if the patient was not enrolled in the study. If the surgeon chooses not to use the RTI technique then this would be noted as a deviation in plan, the reasons recorded and the patient would be excluded from the study without post-operative imaging and their pre-operative and intra operative data would be

analyzed for the purpose of understanding the reasons for failure of the RTI technology to provide assistance for refinement of the technology.

Detailed Study Design:

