The study will enroll 20 patients directly into the RTI group. We will have two surgeons with experience in shoulder arthroplasty and the RTI and SmartBones technology. We will require a minimum of five patients from any one surgeon. All patients will have the standard of care indications for an anatomic total shoulder arthroplasty and will give informed consent for both the surgery and participation in this study. Consent and enrollment will be obtained by the surgeon during a routine office evaluation. All patients will get standard of care pre-operative x-rays and CT scan at least three weeks prior to surgery. Scan quality must meet study specific criteria and we expect that the scans will be performed at the Cleveland Clinic. The pre-operative CT scan will be placed within our pre-operative planning software (OrthoVis Cleveland Clinic). The surgeon will use this software to assess the glenoid bone pathology and select the optimal implant and placement of that implant.

Patients will have standard of care indications for primary anatomic arthroplasty and be able to get a pre-operative shoulder CT scan at the Cleveland Clinic or at an outside facility so long as the study includes the entire scapula and has 1mm or thinner sections. These parameters are required for accurate pre-operative planning as well as comparison with the post-operative CT scans. Standard of care pre- and post-operative x-rays (AP and axillary views) will also be obtained and can be performed at the Cleveland Clinic or acquired from another health care facility. In all patients the standard x-rays and CT images provided by the radiology department will be available to the surgeon before and during the surgery.

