properly determine the quality of the bone stock surrounding the implant. Further correlating this with RSA and 3D CT imaging of implant movement, we can fully develop cause and effect of bone quality on glenoid component loosening.

The participating surgeons will be [name] and [name]. Patients may have surgery at either Cleveland Clinic main campus or at Euclid Hospital. If the procedure is performed at Euclid Hospital, post-operative CT scan and RSA (if chosen), will need to be taken at main campus within 3 weeks. The patient will be made aware of this at the time of enrollment and consent.

Inclusion/Exclusion Criteria:

To be eligible for inclusion, a primary anatomic total shoulder arthroplasty must be indicated for the patient.

Outcome Measures:

By comparing computer generated pre-operative plan to post op component placement, we will be looking at three outcomes. First, the overall difference in component placement between standard of care instrumentation, intelligent reusable instrument (IRB#12-997), patient specific instruments (IRB #10-582) and real time instrumentation will be compared. Secondly, we will compare the placement between the technologies within and between surgeons. Thirdly, we will evaluate the difference in implant position between technologies based on severity of pathology. The quality of the bone core sampled will be correlated to the possible loosening of the implants.

Sample Size:

We expect to enroll 20 patients for this clinical case series. Data collected will be analyzed in association with the enrollees from IRB#12-997 and IRB#10-582.

Statistical Methods

Average deviations from plan for the RTI, IRI, and freehand groups will be compared using mixed-effects ANOVA methods. Random effects will be included to account for correlation between observations introduced as a consequence of multiple observations of deviation being taken on a particular surgeon. If significant differences are found, multiple comparisons based on the ANOVA model will be made to compare each pair of groups, and will use Holm's step-down procedure to control the family-wise error rate of the tests.

All analyses will be done using R software (version 3.0.0, Vienna, Austria). A significance level of 5% will be used for all testing.

Data Sheets

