Clinical data collected pre and post-operative will be Passive and Active range of motion, manual muscle strength testing and shoulder functional scores, and co-morbidities all of which are standard of care. Post-operative data will be collected at two years (\pm 1 month) after surgery. We will collect at the time of surgery the implant used, the time for surgical care glenoid exposure to end of pin placement. The implant used, the surgical instruments used and any comments from the surgeon as to the ease of use and accuracy of the RTI instruments. Verbatim comments will be solicited and recorded by a research assistant attending all surgical procedures.

Pre-operative imaging data will include: Glenoid version and inclination, estimated pre morbid inclination, version and depth of glenoid bone loss using the glenoid vault model. Preferred implant type inclination and version.

Post-operative implant placement to desired location will be defined for location of the center peg of the implant in the SI, AP and ML dimension in millimeters and the trajectory of the center peg actual vs plan in version and inclination. The location of the implant in relation to the joint line as measured by the glenoid vault model will be measured in millimeters. Back side contact of the implant to the bone will be measured as a surface area in direct contact with the bone and any lucent lines around the implant pegs will be measured. Peg perforation and the location of the peg perforation will be recorded. The tantalum beads within each implant will be measured for translational or rotational movement.

Changes in implant position from post-operative CT scan 1 vs CT Scan 2 will be correlated with back side seating, implant type, medialization of the joint line and peg perforation and severity of the post-operative pathology.

Study data will be collected and managed using REDCap (Research Electronic Data Capture).

[Adverse Events and Data Monitoring Committee \(DMC\):](#)

A Data Monitoring Committee will not be used. Patient safety will be protected by following surgical standards of care. The IRB will be notified in writing of any adverse clinical event related to the use of the IRI or the standard instrumentation. Adverse events include excessive bleeding, infection, fracture nerve injury or need for revision surgery during the term of this study which is expected to be approximately 1 year from the time of surgery.

Consent:

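### The correlations of implant movement and loosening fall under an uncorrected 5% rule, with no lead analysis and no exploratory label

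*Combined protocol and SAP*

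**What the plan says.** Statistical Methods describes one analysis: a mixed-effects ANOVA of deviation from plan across instrument groups. If it is significant, each pair of groups is compared, and these comparisons "will use Holm's step-down procedure to control the family-wise error rate of the tests". The section closes with "A significance level of 5% will be used for all testing", and exempts nothing from that rule.

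The correlations are planned in other sections:

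- **Data Sheets:** change in implant position between the two post-operative CT scans "will be correlated with back side seating, implant type, medialization of the joint line and peg perforation and severity of the post-operative pathology". That makes five factors. The same section records placement against plan "in the SI, AP and ML dimension in millimeters and the trajectory of the center peg actual vs plan in version and inclination", and has the beads in the implant measured for translation and rotation.
- **Bone Quality Measurements:** "all bone quality measurements will be correlated with CT scan imaging of the glenoid at the time of surgery", and again at two years. The humeral sample gives trabecular bone volume, connectivity and a mechanical test.
- **Detailed Study Design:** quantitative CT adds volumetric density and the trabecular network of the glenoid. Bone quality is then related to movement on RSA and CT, with the stated expectation of a full cause-and-effect account of loosening.
- **Outcome Measures:** the three numbered outcomes all concern component placement. A further, unnumbered sentence relates bone-core quality to possible loosening.

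No section names a correlation method, a lead movement measure or a lead bone-quality measure. None calls these analyses exploratory.

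**The concern.** The plan controls error for the group pairs but not for the loosening correlations, although the 5% rule covers both. With several predictors, possibly several movement measures and no lead, the analyst can choose after seeing the data which correlation to stress. The stated aim is causal, so a chance result could be published as a cause of glenoid loosening and influence later work on implants or patient selection.

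The small series adds a separate problem. Only a large sample correlation can reach significance, so a modest true association that does reach it will be overstated.

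**Working it through.** **Inputs**

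- Level: 5% per test (Statistical Methods). Two-sided is assumed, because sidedness is not stated.
- Surgical factors: 5 (Data Sheets).
- Bone-quality measures: about 5, namely volumetric density, glenoid trabecular network, humeral trabecular volume, connectivity and mechanical testing (Bone Quality Measurements; Detailed Study Design).
- Movement measures: not fixed by the documents. The range assumed is from 1 summary to 7 components (SI, AP, ML, version and inclination on CT; translation and rotation on RSA).
- Patients: "The study will enroll 20 patients directly into the RTI group" (Detailed Study Design).

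The plan gives no test count or error rate for these correlations, so there is no figure of its own to reproduce.

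**Number of tests, k (assumed)**

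- One movement summary: 5 × 1 + 5 × 1 = 10.
- One CT and one RSA summary, with surgical factors against CT only: 5 × 1 + 5 × 2 = 15.
- Each component separately: 5 × 5 + 5 × 7 = 25 + 35 = 60.

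**False positives if every null hypothesis is true**

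The expected number is 0.05 × k, whatever the dependence between tests. The chance of at least one, if the tests are independent, is 1 − 0.95^k.

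| k | Expected | At least one, independent |
|---|---|---|
| 10 | 0.50 | 40% |
| 15 | 0.75 | 54% |
| 25 (surgical factors by CT axes only) | 1.25 | 72% |
| 60 | 3.0 | 95% |

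**Correlated measures**

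Correlation among the measures leaves the expected number unchanged but lowers the chance of at least one. These figures are simulated at n = 20, with an assumed common correlation within each set of measures:

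- 10 predictors by one summary: about 29% at 0.5.
- 5 × 5 grid: 72%, 67%, 55% and 40% at 0, 0.3, 0.5 and 0.7.
- 10 × 7 grid (70 tests, the nearest full grid to the 60): 97%, 94%, 84% and 61% at the same values.

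**Size of correlation needed**

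For continuous measures, critical |r| = t / √(n − 2 + t²), with t the two-sided 5% point on n − 2 degrees of freedom.

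- n = 20: 2.101 / √(18 + 4.414) = 0.44.
- n = 15: 2.160 / √(13 + 4.667) = 0.51.

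**Power**

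For an assumed true r of 0.5 at n = 20, power by Fisher's z is about Φ[(atanh 0.5 − atanh r_crit) × √17].

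- One test at 5% (r_crit 0.444): Φ(0.30) = 62%.
- First Holm step over 25 tests (level 0.05 / 25 = 0.002, r_crit 0.648): Φ(−0.92) = 18%.

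**The case against.** A reader might infer that the plan commits to dozens of tests, so that false findings are to be expected. The documents do not support this. Data Sheets lists the five axes to define placement against plan, and the separate correlation sentence speaks only of change in implant position. Carrying the axes over is plausible but is an inference. With one movement summary there are about 10 tests and 0.5 false positives expected, which is below one. The figures also assume that every null hypothesis is true, whereas the Overall Summary starts from the premise that loosening is associated with malposition and bone quality. These objections stand, so the size must be given as a range.

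The limit of 20 patients can also be questioned, because Sample Size says "Data collected will be analyzed in association with the enrollees from IRB#12-997 and IRB#10-582". Pooling is not stated for these correlations, nor is it excluded. A larger sample would lower the critical |r| but not the number of false positives expected. In the other direction, numbers fall where RSA was not chosen, where quantitative CT was unavailable, or where the patient was excluded because the RTI mold was not used. The critical |r| does not apply to implant type, which is categorical, or to peg perforation if it is recorded as yes or no.

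Finally, unadjusted secondary correlations are common in a case series, and the numbered outcomes concern placement. That is a good reason to label the correlations exploratory. It does not justify a 5% test combined with a causal aim.

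**Conclusion.** The concern holds as a minor one. The 5% rule covers the movement and bone-quality correlations, Holm's procedure does not reach them, no lead is named, and the protocol states a causal aim for them.

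The size depends on a test count that the documents leave open. Over the assumed range of 10 to 60 tests, 0.5 to 3.0 false positives are expected if all nulls are true, and the chance of at least one is 40% to 95% under independence. Correlated measures reduce that chance. The within-set correlations used above are assumptions, as is two-sided testing.

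The point does not extend to the comparison of instrument groups, whose pairwise tests are covered by Holm's procedure.

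**What to change.** In Statistical Methods, state that the 5% rule applies to the technology contrasts and, if the investigators want one, to a single pre-named lead correlation tested at two-sided 5%. The lead should use measures that do not depend on optional imaging. An example is total translation from the first to the second CT scan against micro-CT trabecular bone volume of the humeral sample. An RSA-based lead would be limited to the patients who chose RSA.

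Report all other movement and bone-quality correlations as exploratory estimates with 95% confidence intervals and no claim of significance. In Detailed Study Design, replace the cause-and-effect wording with association.

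This changes wording only and needs no new patients, scans or data. The downside is that fewer results can be called significant. Holm's procedure across the whole family would also control the error, but the working shows the loss of power: 18% at its first step over 25 tests, against 62% for one named test.

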Using the Smartbone surrogate model, the surgeon visually compares the exposed glenoid surface to the Smartbone model to ensure that the two match for size and shape. Any adjustments to the surgical site may be done by the surgeon to optimize the match between the model and the exposed glenoid surface. Prior to molding the bone cement, bone wax is wiped onto the model to ensure proper release of the cement mold. The surgeon will then mold bone cement around the pin in the Smartbone, capturing the trajectory of the pin and the unique contours of the glenoid rim. A small pin sleeve is inserted over the pin to be embedded within the cement model. Once the bone cement has cured, it is removed from the model and placed onto the patient's glenoid surface. The bone morphology captured in the mold aligns the mold to the patient's anatomy. When surgeon feels that the model has good fit of the glenoid surface, he may continue with pin placement. After placement of the guide pin, the RTI mold is removed and the remainder of the procedure is completed using the implant manufacturer's equipment and standard surgical protocols. Any adjustments in guide pin position can be performed by the surgeon based upon surgical judgment. The surgeon can make any change needed and use any means or instrument that would otherwise be used for standard of care surgery to place the guide pin in any position that the surgeon believed to be best for the patient. If the pin is changed without the use of the RTI then the patient will be excluded from this study and the reasons for failure of the RTI technology to provide accurate pin placement based upon the surgeon's sole determination of accuracy will be recorded and later analyzed as a failure to treat. These patients will not receive post-operative CT Scans as we would not be able to use the data.

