Post operatively, all patients will receive a CT with MAR and RSA (if chosen) within 3 weeks of surgery. This will be a CT Scan performed with the patients arm by the side in a supine position using metal artifact reduction techniques. In addition patients will receive a second CT scan RSA imaging, provided they originally got RSA, performed 2 years (\pm 1 month) from surgery. The second CT scan will be performed with MAR techniques and with the patient in the lateral decubitus position with their arm in the overhead position again using metal artifact reduction techniques. The second set of images produce with a different body and arm position also decreases metal artifact than those obtained with the arm placed by the side. This position cannot be comfortably obtained until 3- 6 months after surgery and require healing of the tissues and rehabilitation of the shoulder. We have shown that in a small number of patients the glenoid component can shift in position within the first 3-6 months after surgery making the first CT Scan more accurate for implant position. The images obtained from the post-operative CT scans are placed back into the surgical software and the 3D reconstruction of the post-operative scapula with the implants is compared to the pre-operative plan. Using measurement tools within the software, developed at the Cleveland Clinic, we will compare the position of the actual glenoid component placed in the patient with the desired position specified by the plan. The use and validation of these imaging methods to precisely measure implant position has been performed at the Cleveland Clinic in a prior IRB approved clinical trial (IRB 10-582).

Preoperatively, the high resolution quantitative CT will measure volumetric bone mineral density and the trabecular network of the glenoid. When available, this will be applied to the preoperative CT for those patients at Main Campus. Patients who have their preoperative CT completed at non Main Campus facilities will have the standard of care preoperative CT. This will be done at same visit for the standard of care pre-operative CT. Micro CT imaging, which creates a 3D reconstruction of the fine bone structure, in addition to microarchitecture analysis and mechanical testing, will allow assessment of the bone tissue taken from the bone core sample. Between the preoperative imaging and the bone tissue analysis, we will have data to

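### Placement accuracy is defined by five deviations with no primary measure or composite, and Holm covers only group pairs, so error across the measures is uncontrolled

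*Combined protocol and SAP*

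**What the plan says.** Outcome Measures states that "we will be looking at three outcomes. First, the overall difference in component placement between standard of care instrumentation", IRI, PSI and RTI will be compared. The outcomes are numbered, but none is called primary, and the section does not say how an overall difference is formed.

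Data Sheets gives the only definition of placement against plan: "center peg of the implant in the SI, AP and ML dimension in millimeters and the trajectory of the center peg actual vs plan". Trajectory there means version and inclination. That makes five deviations, three in millimetres and two of direction. A further position measure follows: "The location of the implant in relation to the joint line as measured by the glenoid vault model will be measured in millimeters".

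Statistical Methods says: "Average deviations from plan for the RTI, IRI, and freehand groups will be compared using mixed-effects ANOVA methods". It does not say which deviation, or whether it is signed or absolute. If the ANOVA is significant, "multiple comparisons based on the ANOVA model will be made to compare each pair of groups, and will use Holm's step-down procedure". The section ends: "A significance level of 5% will be used for all testing".

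**The concern.** Millimetres and degrees cannot be averaged together without a scaling rule, and none is given. Someone following the plan must therefore either run an ANOVA for each measure or choose a summary, and nothing prevents that choice being made after the data are seen.

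Holm protects the pairwise comparisons within one ANOVA. It gives no protection across several ANOVAs on different measures, each at 5%. The family-wise control that the plan sets out therefore does not reach its own first outcome. At stake is the main claim of the study: a chance difference on one of five measures could be reported as a difference in placement accuracy for RTI.

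**Working it through.** The plan contains no derived figure to reproduce. The 20 patients come without an effect size, SD or power, and 5% is a per-test level.

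**Inputs from the documents**
- Level per test: 0.05 (Statistical Methods).
- Number of deviations from plan: k = 5 (Data Sheets). One combined distance and one combined angle would give k = 2.
- Groups: three in Statistical Methods (RTI, IRI, freehand), giving 3 pairs; four in Outcome Measures (PSI added), giving 6 pairs.
- RTI group: 20 patients (Sample Size).

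**Assumptions, because the documents are silent**
- 20 patients in every group, normal data, and the surgeon effect left out.
- Equal correlation between measures, from 0 to 0.8.
- No true difference on any measure.

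**Step 1. At least one false ANOVA, independent measures:** 1 − (1 − 0.05)^k.
- k = 1: 5%.
- k = 2: 1 − 0.95² = 9.75%.
- k = 5: 1 − 0.95⁵ = 22.6%.

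**Step 2. Correlation, and the narrower RTI event.** I used simulation with 10,000 runs per setting. Each measure has an ANOVA at 5%; if it is significant, Holm is applied over the group pairs. The RTI event is that at least one pair including RTI is declared different on at least one of the five measures.

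| Correlation | Any false ANOVA, 3 groups | Any false ANOVA, 4 groups | RTI pair, 3 groups | RTI pair, 4 groups |
|---|---|---|---|---|
| 0 | 22.2% | 22.4% | 14.3% | 10.1% |
| 0.3 | 20.8% | 21.6% | 13.8% | 10.0% |
| 0.5 | 19.2% | 18.7% | 12.8% | 9.0% |
| 0.8 | 13.4% | 13.7% | 9.1% | 6.6% |

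For a single measure the RTI event has a chance of about 3% with three groups and 2% with four. As a check at independence, 1 − (1 − 0.03)⁵ = 14.1% and 1 − (1 − 0.02)⁵ = 9.6%, which agree with the first row. With about a point of allowance for simulation error, correlation 0.5 to 0 gives 13-15% (three groups) and 8-10% (four groups).

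**Step 3. After the fix.** With no true difference, Holm's first threshold decides whether anything is declared.
- Five measures: 0.05/5 = 0.0100, and 1 − 0.99⁵ = 4.9%.
- Two measures: 0.05/2 = 0.025, and 1 − 0.975² = 4.9%.
- Five measures at correlation 0.5: about 4% by simulation, with three or four groups.

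**The case against.** The best reply is that the plan does not prescribe five ANOVAs. The word overall may mean a summary: SI, AP and ML can form one distance, and version and inclination one angle. That reply stands in part. It brings the chance of a false ANOVA down to 9.75% if the two are independent, but no summary is written down, so the choice stays open and even two measures need a rule. It is also true that Holm does what is promised within one ANOVA, and that strict control across measures is not obligatory in a small non-randomized case series. But this plan chooses formal tests and family-wise control, so it should say which tests form the family.

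A reader might infer four stronger points that the documents do not support.

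- **22.6% is the chance of a false claim about RTI.** It is not. It counts any significant ANOVA, including one driven by other groups and one after which no pair survives Holm. The RTI event is smaller, and only about half of it would favour RTI.
- **Joint-line location is a sixth deviation, making it 26.5%.** Data Sheets does not describe it as a deviation from plan.
- **ML depth cannot reflect RTI because the pin does not set it.** Detailed Study Design says only: "After placement of the guide pin, the RTI mold is removed and the remainder of the procedure is completed using the implant manufacturer's equipment". Those later steps come before the final position on every axis, so the sentence does not separate ML from the rest, and no section says what sets depth.
- **Accuracy will be read at two years and mixed with migration.** Detailed Study Design says that in a few patients "the glenoid component can shift in position within the first 3-6 months after surgery making the first CT Scan more accurate for implant position", and Data Sheets uses the second scan for change from the first. The first scan is evidently meant; the plan need only say so.

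**Conclusion.** The concern holds as a gap in specification and multiplicity. Placement against plan has five measures, none primary and no composite, and the stated error control stops at group pairs. If all five are tested, the chance of at least one false ANOVA is 22.6% under independence and about 19% at correlation 0.5. The chance of a false RTI pair is about 13-15% with three groups or 8-10% with four, roughly four to five times the single-measure figures of 3% and 2%.

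These sizes rest on 20 patients per group, no surgeon effect, and correlations that the documents do not give. At correlation 0.8 the RTI figures fall to about 9% and 7%, still about three times the single-measure rate. The second and third outcomes (by surgeon and by severity) are not counted. The depth, joint-line and two-year readings do not stand as errors.

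**What to change.** In Outcome Measures and Statistical Methods:

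1. Name the primary accuracy measure or measures. One option is a 3D centre-peg distance and a single trajectory angle; the other is to keep the five deviations. State that they are absolute deviations, since signed ones can average to zero in a group that is often far from plan.
2. Apply Holm across the ANOVA tests of the primary measures (first threshold 0.025 for two, 0.0100 for five). Make the Holm-adjusted pairwise comparisons only for measures that pass.
3. Report every other position measure as secondary and descriptive.
4. State that accuracy is read on the first post-operative CT.
5. Use the same list of groups in both sections, so that the set of pairs is fixed.

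Whether ML depth belongs among the primary measures is for the investigators to decide. Step 2 controls the ANOVA claims. If strict control over all pairs and measures jointly is wanted, they need one Holm family: with three groups, 2 × 3 = 6 tests (smallest threshold 0.05/6 = 0.0083) or 5 × 3 = 15 (0.05/15 = 0.0033).

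The change needs no new data. Its cost is a stricter threshold per measure and some loss of power with 20 RTI patients. That loss cannot be quantified, because the plan gives no effect size or SD. It is smaller with two primary measures than with five.
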